2.4 Other endpoints

- At least one treatment-emergent systemic allergic reaction including anaphylaxis¹⁷
- At least one TEAE treated with adrenaline/epinephrine
- At least one treatment-emergent severe local swelling or oedema of the mouth and/or throat
- A TEAE of eosinophilic oesophagitis
- A TEAE leading to discontinuation
- Daily duration of recurrent TEAEs

¹⁷ The definition of anaphylaxis according to (Sampson et al. 2006), see section 12

3 TRIAL DESIGN

3.1 Summary of trial design

This is a 28-day, single-armed, open-label, multi-centre trial in adolescent subjects (12-17 years of age) with HDM AR/C, with or without asthma.

[figure not shown]
Approximately 250 subjects will be enrolled to receive daily treatment with the HDM SLIT-tablet (12 SQ-HDM).

The trial consists of three trial periods: a screening period, a 28-day open-label treatment period and a 5-7-day follow-up period (see Figure 1).

Each subject will participate in three in-clinic visits: screening (V1), enrolment and first tablet administration (V2), and a final visit (V3). In addition, a telephone contact 7-9 days after V2 and a follow-up telephone contact 5-7 days after intake of last IMP dose will take place.

An unscheduled visit may take place in case of technical issues with lab samples and/or need for safety follow-up.

Figure 1 Trial design

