Primary completion date	Date of the last data collection for the primary endpoint (ClinicalTrials.gov), which is the date of the last contact (FU-TC) for the last subject in the trial globally
Solicited AE	A pre-specified AE recorded by the investigator based on the signs/symptoms reported in the subject's diary during the 28 days of treatment

Source documents	Source documents are original documents, data, and records from which the subjects' electronic case report form (eCRF) data are obtained. These include, but are not limited to, hospital records (from which medical history and concomitant medication may be summarised into the eCRF), clinical and office charts, laboratory and pharmacy records, diaries, microfiches, radiographs, and correspondence
Systemic allergic reaction	Allergic reactions occurring after exposure to an allergen with symptoms from one or more organ system (skin, mucosal, respiratory, cardiovascular or gastrointestinal) not related to the administration site. Systemic allergic reactions can occur in different grades with the most severe reactions being anaphylaxis
Systemic corticosteroids	Oral, intramuscular, or intravenously administered corticosteroids
TEAE	TEAEs are defined as adverse events with start date on or after the time of first IMP administration and no later than 7 days after last IMP administration
Trial completion	The trial is completed once the integrated clinical trial report (ICTR) is signed
Subject discontinuation date	Date of subject trial discontinuation. In case of subjects lost to follow-up, the discontinuation date is defined as the date the investigator/sponsor decides to discontinue the subject

Protocol versions

Date	Version	Description of document	Rationale for amendment
06-Feb-2020	1.0	Final Protocol	N/A
08-Apr-2020	2.0	
Amendment 1: Amendment to address:
 
• risks associated with the COVID-19 pandemic• specific allergen used in the Skin Prick Test (SPT). 
The amendment applies to all countries. There are no changes affecting subject information and assent forms.
	
Amendment is done to address the EMA recommendations in the Guidance on the Management of Clinical Trials during the COVID-19 (Coronavirus) pandemic Version 2 (27/03/2020).
 
In addition, allergen for the SPT, is revised, please refer to rationale in the table below.

Section # and name	Description of change	Brief rationale

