1.4 benefit-risk assessment	A section including COVID-19 related risk in context of this trial is inserted	According to latest guidelines, Sponsor needs to address additional COVID-19 related risks to participants in the risk benefit section of the protocol.
11.13 Skin prick test	The mould allergen; Cladosporium herbarum is removed from SPT	The primary objective of this trial is to evaluate safety and tolerability during 28-days of treatment with HDM SLIT-tablet. From a clinical point of view the specific results of the SPT for moulds will have minimal, if any, impact on the overall trial results as well as data integrity and there is no effect on patient safety. The SPT panel will include Alternaria alternata , the most prevalent mould allergen

Flow chart

Trial period:	Screening	Treatment			Post-treatment	
		V2	TC	V3 ¹		
Visit ID:	V1					
Visit title:	Screening	Enrolment and administration of first tablet	Telephone contact	Final visit	Follow-up Telephone contact	Unscheduled Visit
Scheduled day:		Day 1	Day 8	Day 29 ⁴	Last day of treatment + 5-7 days	
Scheduling window:	Max 12 weeks prior to Day 1		+/- 1 day	+ 3 days		
Informed consent/assent	X					
Demography	X					
Smoking habits	X					
Medical history	X					
Previous ⁵ and concomitant medication	X	X	X	X	X	X
Height and weight	X	X				
Vital signs	X	X		X		(X)
FEV ₁ ⁶	X	X		X		(X)
Physical examination	X					(X)
Oropharyngeal examination		X ⁷		X		(X)
Assess symptoms of eosinophilic oesophagitis	X	X	X	X	X	(X)
Urine pregnancy test, if applicable ⁸	X	X		X		(X)
SPT ⁹	X	(X)				
Blood and urine sampling for safety analyses	X					(X)
Assess compliance with Inclusion/exclusion criteria	X	X				

¹ If a subject discontinues prior to completing the 28-day treatment period, the assessments of V3 should be performed 5-7 days after last IMP intake.

² Post-trial treatment with HDM SLIT-tablets must not be initiated before FU-TC has been performed.

³ Assessments at unscheduled visit(s) marked (X) are performed as applicable

⁴ Conducted on Day 29 in order to allow for diary completion for last day of treatment (Day 28)

⁵ Previous medication to be assessed only at V1 and covering at least 1 year.

⁶ Measure Forced expiratory volume in 1 second (FEV₁) and calculate the % of predicted FEV₁.

⁷ Oropharyngeal examinations will be done before IMP administration at V2.

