12 SAFETY

Information about AEs, whether reported by the subject, discovered by the investigator by reviewing diary records, detected through physical examination or other means, must be collected and recorded on the AE form and followed up as appropriate. Evaluation of AEs including severity, causality, outcome and seriousness assessments must be performed by a physician.

³¹ A tongue ulcer is a discrete, painful lesion affecting an area on the tongue, where the mucosa is eroded

Any AE occurring from the time the informed consent was signed by the subject and until the FU-TC must be recorded and reported on the AE page in the eCRF. This includes all AEs, even AEs occurring before the subject is administered the IMP and whether or not AEs are observed in connection with the trial assessments and conduct of the trial. TEAEs are defined as adverse events with start date on or after the time of first IMP administration and no later than 7 days after last IMP administration.

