12.3.4 Follow-up on AEs and SAEs

SAEs must be followed up until resolution and until all queries have been resolved. The investigator must respond to SAE follow-up requests from ALK without delay and no later than 7 days after receiving the request.

Ongoing SAEs can be closed at the FU-TC with the term “not recovered” for chronic diseases (as evaluated upon medical evaluation by the investigator or the sponsor).

The investigator must ensure that the worst-case severity and seriousness of an event is kept throughout the trial.

Non-serious AEs must be followed up until resolution or until the FU-TC.

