15.8 Safety analyses

The evaluation of safety results will be based on TEAEs. TEAEs are defined as adverse events with start date on or after the time of first IMP administration and no later than 7 days after last IMP administration.

No statistical hypothesis testing will be performed.

All adverse events occurring in the trial including non-TEAEs will be listed.

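### AE recording may stop up to 2 days before the 7-day TEAE window closes, and the follow-up call that ends it is dated from two different anchors

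*Combined protocol and SAP*

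**What the plan says.** **TEAE window.** The Table of definitions, section 12 and section 15.8 all count AEs that start from first IMP intake and "no later than 7 days after last IMP administration". Section 15.8 adds: "The evaluation of safety results will be based on TEAEs". The primary endpoint is at least one TEAE (section 2.2).

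**End of recording.** Section 12 states "Any AE occurring from the time the informed consent was signed by the subject and until the FU-TC must be recorded", and section 12.3.4 states "Non-serious AEs must be followed up until resolution or until the FU-TC". The Table of definitions also makes the FU-TC the last data collection for the primary endpoint. After it, section 12.3.8 asks only for IMP-related SAEs and pregnancies that come to the investigator's attention.

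**Timing of the call, counted from last dose.** Section 3.1 has "a follow-up telephone contact 5-7 days after intake of last IMP dose will take place". The flow chart has "Last day of treatment + 5-7 days". Section 3.2 gives the same 5-7 day follow-up and its reason.

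**Timing of the call, counted from visit 3.** Table 2 (section 10), in the visit 3 entry, has the site book the call 5-7 days later. The synopsis puts it about 7 days after visit 3. Section 11 sends sites to both the flow chart and section 10 for timing.

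**Early stoppers.** Flow chart footnote 1 and section 5.1 place the visit 3 assessments 5-7 days after last IMP intake.

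**The concern.** The endpoint window and the data collection window should end together, or collection should end later. Here a site that follows section 3.1 exactly can close AE recording on day 5 while the primary endpoint counts events to day 7. A non-serious event, or an unrelated serious one, that starts on day 6 or 7 is a TEAE by definition, but no planned contact would pick it up. The error can only lower the counts, in a trial whose sole objective is safety.

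The two anchors are a separate defect. For some permitted visit 3 dates a site cannot satisfy both the flow chart and Table 2. The same call also fixes the upper age limit in I2, the end of the Table 1 medication windows and the earliest start of post-trial treatment, so the ambiguity reaches beyond AE collection.

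For early stoppers, the visit falls on the same days as the flow chart's follow-up call, and section 5.1 does not say whether it replaces the call.

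Some things are not at stake. Solicited AEs are confined to the 28 treatment days (Table of definitions; Appendix 5, section 1). AEs starting after day 7 are not TEAEs. With one arm and no hypothesis test, no between-group comparison is biased.

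**Working it through.** **Inputs.** Last dose Day 28 and visit 3 on Day 29 (flow chart footnote 4); visit 3 window +3 days, so Days 29-32 (flow chart); TEAE window to last IMP + 7 (sections 12, 15.8); call at last IMP + 5 to 7 (flow chart, 3.1) or visit 3 + 5 to 7 (Table 2); 250 subjects (section 15.1). The plan gives no figure of its own to reproduce here.

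**Step 1: days without collection.** The TEAE window is Day 1 to Day 28 + 7 = Day 35, so 35 days. The last-dose anchor gives a call on Days 33-35. Counting the call day as observed:

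- call on Day 33: 35 − 33 = 2 days lost, 2/35 = 5.7%
- call on Day 34: 1 day lost, 1/35 = 2.9%
- call on Day 35: none

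**Step 2: do the two anchors agree?** (last dose on Day 28)

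| Visit 3 | Table 2 call | Shared with Days 33-35 | Days lost under Table 2 |
|---|---|---|---|
| Day 29 | 34-36 | 34, 35 | 1 if called on Day 34, else 0 |
| Day 30 | 35-37 | 35 | 0 |
| Day 31 | 36-38 | none | 0 |
| Day 32 | 37-39 | none | 0 |

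The synopsis taken literally (visit 3 + 7) gives Days 36-39, always outside Days 33-35, although its wording is approximate. The result depends on the last dose day: with a last dose on Day 29 only visit 3 on Day 32 has no shared day, and with a last dose on Day 30 or later there is always one.

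**Step 3: early stoppers.** With last dose on day L, both the visit and the flow chart's call fall on L+5 to L+7. If the visit is the closing contact, 0 to 2 of L+7 days are lost (for L = 7, up to 2 of 14). Table 2 read literally puts a call at L+10 to L+14, which covers the window.

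**Step 4: size of the undercount.** The documents give no event rate for days 6-7 after last dose, so this is a bounding model. Assume hazard h on Days 1-28 and r·h on Days 29-35. For a call on day c,

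S(c) = exp{−h[28 + r(c − 28)]}, loss = S(c) − S(35),

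and h is chosen to make the loss as large as possible.

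For r = 1 and c = 33, the maximum is at h = ln(35/33)/2 = 0.0294. Then S(33) = 0.3787, S(35) = 0.3571 and the loss is 0.0216, at a TEAE proportion of 0.64.

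| r (assumed) | All calls on Day 33 | Calls even over Days 33-35 (assumed) |
|---|---|---|
| 1 | 2.16 points, 5.4 of 250 | 1.08 points, 2.7 of 250 |
| 0.25 | 0.62 points, 1.6 of 250 | 0.31 points, 0.8 of 250 |
| 0.10 | 0.26 points, 0.6 of 250 | 0.13 points, 0.3 of 250 |

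If 90% of subjects have a TEAE (assumption) and calls are even, the loss falls to 0.20 points (0.5 of 250) at r = 0.25 and 0.08 points (0.2 of 250) at r = 0.10.

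**The case against.** The strongest reply is that the short follow-up was a reasoned choice. Section 3.2 says few AEs have followed end of treatment in earlier trials and that most of those came in the first few days. On this view the 7-day limit only classifies onset dates and promises no seven observed days per subject. A compliant date also exists on the planned schedule: with visit 3 on Day 29, a call on Day 35 satisfies the flow chart, section 3.1 and Table 2, is 6 days after visit 3, and loses no full day. Finally, the undercount is far smaller than the sampling error: at 64% with 250 subjects the 95% half-width is about 1.96 × √(0.64 × 0.36/250) = 6 points.

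Much of this stands. The effect is negligible beside the confidence interval, and the constant-hazard case runs against section 3.2. The 2-day gap exists only under the last-dose anchor; Table 2 loses at most 1 day. The early-stopper gap depends on reading the visit as the closing contact, although the flow chart keeps the call as a separate column. A subject who stops because of a TEAE has already met the primary endpoint.

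What it does not answer is why collection may end before the endpoint's own window, or which anchor a site must follow. Nothing requires the Day 35 call, and for visit 3 on Day 31 or 32 no common date exists when the last dose is on Day 28.

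A cheaper repair would end the TEAE window at the call. That removes the mismatch, but the window would then vary between subjects with the call date, and the two anchors would still need reconciling.

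**Conclusion.** The concern holds and should be corrected. As written, routine AE recording can end 1 or 2 days before the TEAE window closes, and the contact that ends it has two dates that cannot always both be met. Both results are calendar arithmetic for a last dose on Day 28.

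The effect on the primary endpoint is very small and only downward: a ceiling of 2.2 points (about 5 of 250), and 0.13 to 0.31 points if the off-treatment hazard is 10-25% of the on-treatment hazard and calls are spread evenly. Those hazard ratios and the even spread are assumptions. IMP-related SAEs reported after the call are a partial exception to the gap. The case for change rests on an inconsistent cut-off for a safety endpoint, not on a material bias.

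**What to change.** Give one FU-TC timing in the synopsis, flow chart, sections 3.1 and 3.2 and Table 2. Count it from last IMP intake, place it after the 7-day TEAE window has closed, and state its latest day. A call on day 7 still misses the rest of that day; a call from day 8 does not. As an example, days 8-10 keep the present 3-day width. For a last dose on Day 28 that is Days 36-38, and Table 2 already permits at least one of those days for each visit 3 date: Day 36 for Day 29, Days 36-37 for Day 30, Days 36-38 for Day 31 and Days 37-38 for Day 32.

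In section 5.1, state which contact ends AE recording for early stoppers, and make sure it also covers the 7-day window.

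The passages tied to the FU-TC must be reconciled with whatever timing is kept: the I2 age limit, the Table 1 windows, the start of post-trial treatment and the early-discontinuation visit.

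**Cost.** A wording amendment and a later phone call. A call on day 8 is 3, 2 or 1 days later than one on day 5, 6 or 7. With the 3-day width kept, the latest permitted day moves from 7 to 10, so one subject's call could move by up to 5 days. Rules that end at the FU-TC would lengthen with it unless they are re-anchored. For I2, 3 extra days affect 3/(6 × 365.25) = 0.14% of candidates, about 0.3 of 250, if ages are spread evenly over 12-17 years (assumption). For early stoppers, either the visit passages are reconciled or one closing call is added.

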3.2 Discussion of design

This trial may be conducted throughout the year irrespective of coinciding pollen seasons, as long as the 28-day treatment period does not overlap with the relevant season for the allergen to which the individual subject is allergic. The purpose of this trial is to collect safety data in adolescents with HDM AR/C with or without asthma to supplement existing safety data in this age group.

An open-label trial design is expected to reduce the time of trial conduct since recruitment of the relevant trial population, adolescents (12-17 years of age) with HDM AR/C, is likely to be less challenging as all subjects will receive active treatment.

The single-armed, open-label design also eliminates the ethical considerations of placebo treatment since the efficacy of the active treatment is established. The trial will be conducted in countries in which the HDM SLIT-tablet is authorised for use in the adolescent age group, thereby all subjects will have the opportunity of continuing treatment after trial completion.

To ensure an unbiased selection of subjects and reporting of AEs, if any, subjects must be naïve to treatment with the HDM SLIT-tablet.

A treatment period of 28 days is chosen based on previous experience with the onset of AEs in the HDM SLIT-tablet development programme. Subjects who develop IMP-related AEs generally experience these, if any, within the first few days of treatment, with few new IMP-related AEs occurring beyond the first weeks of treatment. In addition, the proposed treatment duration of 28 days will allow for solicitation of pre-specified AEs identified as events of special interest (ESIs) of SLIT-tablets. In previous trials with this product, few AEs have occurred after end of treatment, and in follow-up periods of up to 14 days, the majority of events have occurred in the first few days, hence, as the safety profile of the HDM SLIT-tablet is well established a follow-up period of 5-7 days is chosen after last day of treatment.

It is expected that the proportion of reported AEs will be higher in this trial compared to previous trials due to the open-label design and active solicitation.

3.3 Justification of dose

The active dosage chosen in the trial is 12 SQ-HDM, which is the approved dose for adults in the United States, Canada, Europe, Australia, New Zealand, Russia, and Southeast Asia, and for adolescents (12-17 years) in Europe, Australia, Russia and Southeast Asia. The selected dose for this trial, is based on phase I safety data in children, as well as the being the appropriate dose established in adults as the dose providing the highest efficacy with the fastest onset of effect and with a safety profile that supports daily at-home administration (Demoly et al. 2016; Nolte et al. 2015; Virchow et al. 2016). This dose (12 SQ-HDM) is intended to constitute the relevant dose for all populations \geq 5 years of age, in accordance with the general practice for AIT (Alvarez-Cuesta et al. 2006).

3.4 End of trial definition

A subject is considered to have completed the trial if he/she has completed the treatment period (V3).

The overall end of the trial is defined as the date of last contact (FU-TC) for the last subject in the trial globally.

4 TRIAL POPULATION

Approximately 250 adolescent subjects (12-17 years of age) with HDM allergic rhinitis/rhinoconjunctivitis (AR/C) with or without asthma who meet all inclusion criteria and none of the exclusion criteria will be selected to participate in the trial.

4.1 Inclusion criteria

Subjects are eligible to be included in the trial only if all of the following criteria apply:

- I1. Written informed consent obtained from subjects' legal representatives before any trial related procedures are performed¹⁸
- I2. Male or female subjects aged ≥ 12 to ≤ 17 years on the screening day (visit 1) and at the FU-TC.
- I3. A clinical history of allergic rhinitis/rhinoconjunctivitis (AR/C) when exposed to HDM (diagnosed by a physician) of 1-year duration or more (with or without asthma) and with allergic rhinitis (AR) symptoms despite having received allergy pharmacotherapy during the previous year prior to screening visit (visit 1)¹⁹
- I4. Positive skin prick test (SPT) to *Dermatophagoides pteronyssinus* and/or *Dermatophagoides farinae* at screening (wheal size of ≥ 3 mm)²⁰
- I5. Lung function measured by Forced expiratory volume in 1 second (FEV₁) $\geq 70\%$ of predicted value²¹ or according to local requirements while on subject's usual asthma medication
- I6. The subject must be willing and able to comply with trial protocol and adhere to IMP treatment

4.2 Exclusion criteria

Subjects are excluded from the trial if any of the following criteria apply:

- E1. A clinically relevant history of symptomatic perennial AR/C caused by a perennial allergen source, such as animal hair and dander and/or mould to which the subject is exposed during the 28-day treatment period
- E2. A clinically relevant history of symptomatic seasonal AR/C caused by an allergen to which the subject is exposed, and which could potentially overlap with the 28-day treatment period
- E3. A subject who has previously been included in studies with the HDM SLIT-tablet, or otherwise being treated with the marketed HDM SLIT-tablet (e.g. ACARIZAX, ODACTRA)
- E4. Any SLIT or SCIT treatment with *D. pteronyssinus* or *D. farinae* reaching the maintenance dose within the last 5 years. In addition, any SLIT or SCIT treatment with *D. pteronyssinus* or *D. farinae* within the previous 12 months prior to visit 1
- E5. Ongoing treatment with any allergy immunotherapy (AIT) product at screening

¹⁸ Assent from the subject must be obtained according to national requirements.

¹⁹ The investigator should do everything possible to obtain medical records with documentation for HDM allergic rhinitis. If medical records are not available, verbal history from subject/legal representative can be used to fulfil this criterion and this must be documented in the medical records by the investigator

²⁰ If medication that could interfere with the SPT, according to Table 5, has not been washed out and the positive control is <3 mm, the SPT must be performed/repeated after the interfering medication has been washed out and before enrolment

²¹ Lung function will be measured according to the ATS/ERS spirometry recommendations (Reddel et al. 2009). The subjects will be included based on spirometry values measured at the site and reported by the site according to the site's pre-programmed spirometric reference equations. The reference equations and values used should be documented on every pulmonary function report.

- E6. Severe chronic oral inflammation
- E7. A diagnosis or history of eosinophilic oesophagitis
- E8. Systemic immunosuppressive treatment within 3 months prior to screening
- E9. Any clinical deterioration of asthma that resulted in emergency treatment, hospitalisation or treatment with systemic corticosteroids within 3 months prior to first tablet administration (visit 2)
- E10. Any clinically relevant chronic disease, including malignancy, that in the opinion of the investigator would interfere with the trial evaluations or the safety of the subject
- E11. A history of chronic urticaria (> 6 weeks) and/or chronic angioedema (> 6 weeks) within the last 2 years prior to screening visit that in the opinion of the investigator may constitute an increased safety concern
- E12. A relevant history of systemic allergic reaction e.g. anaphylaxis with cardiorespiratory symptoms, generalised urticaria or severe facial angioedema that in the opinion of the investigator may constitute an increased safety concern
- E13. Active or poorly controlled autoimmune diseases, immune defects, immunodeficiencies, immunosuppression or malignant neoplastic diseases with current disease relevance
- E14. Treatment with an investigational drug within 30 days or 5 half-lives of the drug (whichever is the longest) prior to screening visit
- E15. Known history of allergy, hypersensitivity or intolerance to any of the excipients or active substances of the IMP (except for *D. pteronyssinus* and/or *D. farinae*)
- E16. Female with positive urine pregnancy test, breastfeeding, pregnant or planning to become pregnant within the projected duration of the trial
- E17. Sexually active female of childbearing potential without medically accepted contraceptive method²²
- E18. A business or personal relationship with trial staff or sponsor who is directly involved with the conduct of the trial
- E19. Previously been enrolled into this trial, is participating in this trial at another investigational site or is participating or planning to participate in any other clinical trial during the duration of this trial
- E20. A history or current evidence of any condition, treatment, laboratory values out of range or other circumstance that in the opinion of the investigator are clinically relevant and might expose the subject to risk by participating in the trial, confound the results of the trial, or interfere with the subject's participation for the full duration of the trial

²² For the purpose of this protocol the following contraceptive methods are considered appropriate: oral contraceptives, trans dermal patches or depot injection of a progestogen drug (starting at least 4 weeks prior to IMP administration); double barrier method: condom or occlusive cap (diaphragm or cervical/vault caps) plus spermicidal agent; intrauterine device (IUD), intrauterine system (IUS), implant, or vaginal ring (placed at least 4 weeks prior to IMP administration); or male partner sterilisation (vasectomy with documentation of azoospermia) prior to the female subject's entry into trial and is the sole sexual partner for that female subject. Sexual abstinence is acceptable as contraceptive if it is true abstinence and in line with the usual lifestyle of the subject. Periodic abstinence (e.g., calendar, ovulation, symptothermal, post-ovulation methods) and withdrawal are not acceptable methods of contraception. However, national requirements regarding contraception should always be followed.

E21. Has a condition or requires treatment that may increase the risk of the subject developing severe adverse reactions after adrenaline/epinephrine administration

E22. Treatment with restricted and prohibited concomitant and previous medication listed in Table 1.

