2.2 Primary endpoint

At least one treatment-emergent adverse event (TEAE)

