4.3.1 Rescreening

Screen failures may be rescreened for one of the following reasons:

- if the reason for screening failure is of an administrative character
- if the subject fails to meet the inclusion criterion I3 with regards to the length of HDM allergy history being less than the required one year that may resolve by rescreening later
- if the subject meets exclusion criterion E2 with regards to symptomatic seasonal AR/C that could potentially overlap with the 28-day treatment period, and that may resolve by rescreening later
- in case of technical issues with laboratory samples (e.g. haemolysed or lost).
- issues with prohibited medication/previous medication that may resolve by rescreening later
- in case of oral surgery, including dental extraction and shedding of a deciduous tooth, to allow healing of the oral cavity
- temporary inflammatory conditions in the oral cavity
- upper airway viral infection or other temporary infections

Rescreened subjects will be assigned a new subject number and the subject's legal representative is required to sign a new ICF. Rescreening of an individual subject is allowed only once.

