12.1 Definitions

12.1.1 Adverse events

An AE is any untoward medical occurrence in a clinical trial subject, and which does not necessarily have a causal relationship with the administered IMP.

An AE can therefore be any unfavourable and unintended sign (including e.g. a medication error), symptom, or disease, whether or not considered related to the IMP.

The following events should not be recorded as AEs:

- A pre-planned procedure, e.g. a surgical intervention, unless the condition for which the procedure was planned has worsened since the informed consent form was signed.
- Pre-existing conditions documented as medical history. However, any worsening in severity or frequency of a pre-existing condition during the clinical trial period must be regarded as an AE.

Events of special interest

Selected AEs will be considered events of special interest (ESIs). ESIs are events that are considered critical for the evaluation of the product's safety profile and for which additional data will be collected. ESIs for this trial are:

- Systemic allergic reactions including anaphylaxis³²
- Events treated with adrenaline/epinephrine
- Severe local swelling of the mouth and/or throat
- Eosinophilic oesophagitis

See Appendix 5 for definitions and aggregated preferred terms used to identify ESIs.

³² The definition of anaphylaxis (Sampson et al. 2006) includes any 1 of the following 3 criteria:

1. Acute onset of an illness (minutes to several hours) with involvement of the skin, mucosal tissue, or both (e.g., generalised hives, pruritis, or flushing, or swollen lips, tongue, or uvula) AND either respiratory compromise (e.g., dyspnoea, wheeze-bronchospasm, stridor, reduced PEF, hypoxemia) or reduced BP* or associated symptoms of end-organ dysfunction (e.g., hypotonia [collapse], syncope, incontinence)
2. Two or more of the following that occur rapidly after exposure to a likely allergen for the subject (minutes to several hours):
 - a. Involvement of the skin-mucosal tissue (e.g., generalised hives, itch-flush, swollen lips, tongue, or uvula)
 - b. Respiratory compromise (e.g., dyspnoea, wheeze-bronchospasm, stridor, reduced PEF, hypoxemia)
 - c. Reduced BP* or associated symptoms (e.g., hypotonia [collapse], syncope, incontinence)
 - d. Persistent gastrointestinal symptoms (e.g., crampy abdominal pain, vomiting)
3. Reduced BP after exposure to known allergen for the subject (minutes to several hours): low systolic BP* or greater than 30% decrease in systolic BP

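### The season exclusion covers only the 28 treatment days, but the primary endpoint counts TEAEs for up to 7 more, leaving a small upward bias that aligned wording would remove

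*Combined protocol and SAP*

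**What the plan says.** Three places set the season rule, and all stop at the end of treatment:

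- Section 4.2, E2 excludes clinically relevant seasonal AR/C from an allergen exposure "which could potentially overlap with the 28-day treatment period".
- Section 3.2 allows the trial to run all year "as long as the 28-day treatment period does not overlap with the relevant season for the allergen to which the individual subject is allergic".
- Section 4.3.1 allows rescreening for "symptomatic seasonal AR/C that could potentially overlap with the 28-day treatment period, and that may resolve by rescreening later".

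E1 has the same limit for other perennial sources, "such as animal hair and dander and/or mould to which the subject is exposed during the 28-day treatment period".

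The counting window is longer. Section 15.8, section 12 and the table of definitions all let a TEAE start as late as "no later than 7 days after last IMP administration". Section 12 requires AEs to be recorded until the FU-TC, which the flow chart and section 3.1 place 5-7 days after the last dose. Section 12.1.1 adds that "any worsening in severity or frequency of a pre-existing condition during the clinical trial period must be regarded as an AE". The primary endpoint (section 2.2) is at least one TEAE of any cause, and section 15.8.1 has no rule that sets seasonal events aside.

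Other protections do reach the follow-up contact. I2 applies the age limit at the FU-TC, and most restrictions in Table 1 run until the FU-TC because the medication would interfere with the safety evaluation.

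**The concern.** A subject allergic to birch or grass whose season is expected to open several days after the last tablet satisfies E2 as written. If that subject's rhinoconjunctivitis then flares and the investigator records it as a worsening, its start date makes it treatment-emergent although dosing has ended and another allergen is the cause. In a placebo-controlled trial such events would fall on both arms. Here nothing offsets them, so they raise the reported proportion and appear in the post-treatment part of the onset summaries, where they could be mistaken for late-onset effects of the tablet.

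**Working it through.** The plan gives no figure for this point. Its one sample-size figure, the 0.95% upper limit in section 15.1, reproduces: the exact two-sided 90% upper limit for 1 event in 500 is 0.945%. Nothing below depends on it.

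**1. Length of the gap, last dose on Day 28**

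| | Days | Length |
|---|---|---|
| Season rule | 1-28 | 28 |
| TEAE window by definition (last dose + 7) | 1-35 | 35 |
| TEAE window if the FU-TC is at +5 days | 1-33 | 33 |

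Uncovered share: 7/35 = 20% at most, and 5/33 = 15% if the call comes at +5 days. Table 2 counts the 5-7 days from V3 instead. With V3 on Day 29 that gives Days 34-36, capped at Day 35 by the TEAE definition, so the tail is 6-7 days and stays within the same range. A subject whose last dose is on or before Day 21 has no gap, since 21 + 7 = 28.

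**2. Route from flare to endpoint**

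Season opens in follow-up (not barred by E2) → symptoms worsen and are recorded as an AE (section 12.1.1) → onset is within 7 days of the last dose (section 15.8) → the subject counts towards the primary endpoint, whatever the cause (section 2.2).

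**3. Size**

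Added subjects = N × a × b × q × (1 − p28), where

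- N = 250 (section 15.1);
- a = share with relevant seasonal AR/C, assumed 20-40%;
- b = share of those whose season opens in the follow-up days, assumed 5-15%;
- q = chance that the flare is recorded as an AE, set to 1 (upper bound);
- p28 = share with a TEAE by Day 28, assumed 50-90%.

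Subjects with a season opening in follow-up:

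- low: 250 × 0.20 × 0.05 = 2.5
- high: 250 × 0.40 × 0.15 = 15

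Only those without an earlier TEAE change the primary proportion:

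| p28 | Low | High | Percentage points |
|---|---|---|---|
| 90% | 2.5 × 0.10 = 0.25 | 15 × 0.10 = 1.5 | 0.1-0.6 |
| 80% | 2.5 × 0.20 = 0.5 | 15 × 0.20 = 3 | 0.2-1.2 |
| 50% | 2.5 × 0.50 = 1.25 | 15 × 0.50 = 7.5 | 0.5-3.0 |

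For scale, the exact 95% confidence interval at 200/250 is 74.5% to 84.8%.

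The result is proportional to a × b, which is 1-6% above. If that share were 20%, with p28 = 50% and q = 1, the shift would be 0.20 × 0.50 = 10 points, but one subject in five would then need a season opening in that single week.

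**4. Which outputs are touched**

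- Primary proportion: only through subjects with no TEAE by Day 28.
- TEAE counts, SOC/PT tables and time-to-onset summaries: affected whatever happened earlier.
- Solicited TEAEs: not affected, because Appendix 5 limits them to the 28 treatment days.
- IMP-related AEs: largely shielded by the causality assessment.

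**The case against.** Much of the opposing case stands, and it limits the point.

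- **Other criteria.** A reader might infer that nothing covers the follow-up days. E20 lets the investigator exclude for circumstances that could confound the results, with no 28-day limit. It is a matter of opinion and names no season or window, so it is partial cover.
- **Seasons forecast near Day 28.** E2 speaks of potential overlap, and season onset is not known to the day. A season forecast for Day 29 is therefore already caught on a fair reading. The real gap is later in follow-up.
- **Not every symptom is an AE.** Section 12.1.1 first says that conditions documented as medical history are not recorded as AEs; only a worsening is. Section 11.4 requires a detailed allergy history. Some investigators may treat a usual season as the documented condition, so q may well be below 1.
- **Intent.** A reader might infer that the plan meant to keep seasons out of follow-up as well. Section 3.2 gives no reason for its limit, and 28 days is also the dosing and solicitation period. The FU-TC limits in I2 and Table 1 suggest an oversight but do not prove one.
- **Antihistamines.** A reader might infer that subjects would face the season untreated. Table 1 and section 11.5 bar routine and preventive use but allow as-needed use for acute symptoms.
- **E1.** Perennial exposure is normally already present during treatment, so a gap there needs a new exposure after Day 28. E1 adds little.
- **Harm.** No hypothesis is tested, the endpoint is all-cause by design, TEAEs are also summarised by relationship, and the bias runs against the product. All true. This makes the matter minor but does not remove the mismatch.

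**Conclusion.** The mismatch is real: the season rule ends with the 28-day treatment period and the TEAE window runs 5-7 days further in practice. No analysis rule removes a seasonal flare recorded in those days, and only E20, at the investigator's discretion, could keep such a subject out.

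The effect is an upward, conservative and probably small bias: about 0.25-7.5 of 250 subjects, or 0.1-3 percentage points, given 2.5-15 subjects with a season opening in follow-up and 50-90% with an earlier TEAE. None of these rates is in the documents.

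A reader might put the shift at 1-6 points by dividing 2.5-15 by 250. That treats every such subject as TEAE-free by Day 28. The documents point the other way: section 1.2 describes frequent local events, and section 3.2 expects more AE reporting here than in previous trials. The documents also do not support a claim that the primary endpoint is seriously compromised. This is an inexpensive improvement to make, not a flaw that undermines the trial.

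**What to change.** In E2, section 3.2 and section 4.3.1, replace the reference to the 28-day treatment period with the period from V2 until 7 days after the last IMP dose. Make the same change in E1 for consistency. The exclusion window then equals the TEAE window and the uncovered tail falls from 5-7 days to none.

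The cost is wording in four places, and some co-sensitised subjects scheduled or rescreened about a week earlier or later. No procedure is added, and the planned 250 subjects and the section 15.1 calculation do not change.
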